911 Jewish Health and in Utah, which will review de-identified spirometry data from each study
912 participant. Quality assurance of CT scans will be analyzed by the Imaging Core in Denver.
913 Questionnaires and other data will be quality controlled by the Data Coordinating Center in
914 Denver.

915 As noted above we anticipate that some subjects may expire during the next phase of this study
916 due to a combination of pre-existing disease and the onset of new conditions. These events are
917 not anticipated to be related to the study visit; however, they provide important information
918 about the natural history of COPD and other smoking-related conditions. We will monitor and
919 collect information about deaths in the cohort but will not report them to IRBs as study-related
920 events unless they occur during a study visit or within twenty-four hours of the study visit and
921 are judged to be related to a study procedure.

922 The COPDGene Administrative Core will hire National Research Coordinators. They will visit
923 each Clinical Center periodically to review site facilities, monitor study procedures and record
924 keeping, assist with continuing education of local coordinators to continue our excellent track
925 record of high quality study data and completeness, and as needed and when locally approved,
926 assist in conducting study visits. Clinical centers will be responsible for providing study records
927 and logs for review to the National Research Coordinators.

928 **XI. DATA STORAGE AND DISTRIBUTION**

929 The COPDGene study has nine study cores and twenty participating clinical centers. Clinical
930 centers send data to the Data Coordinating Center (DCC) at National Jewish Health, the
931 Biorepository at Brigham and Women’s Hospital, the Pulmonary Function Testing Center (PFT)
932 at NJH and to the Imaging Center at NJH.

933 The Administrative Center oversees and coordinates all study activities. The DCC maintains
934 confidentiality of all protected health information collected from study participants and stores
935 subject data. The Administrative Center releases data and Biospecimens to internal and external
936 study investigators. Internal Investigators consist of co-investigators at the twenty clinical
937 centers and at the study centers. The Ancillary Studies and Publications Committee oversee
938 distribution of data and Biospecimens to external investigators, outside of the COPDGene study.

939 The Imaging Center receives subject CT scan image files. Data and image files including study
940 dates are shared between three different sites, National Jewish Health, University of Iowa and
941 Brigham and Women’s Hospital, under the Imaging Center.

942 The Pulmonary Function Testing (PFT) Center receives subject data from twenty clinical centers
943 via a file depot located at National Jewish Health provided by the DCC. The PFT Center is
944 located in two locations, at National Jewish Health and reviewed by [name] as a
945 contract consultant, at the University of Utah.

946 The Biorepositories, which collect, store, and distribute blood samples from the twenty centers,
947 are located at Johns Hopkins University and Brigham and Women’s Hospital. The Phase 3
948 samples will be stored at the biorepository at Brigham and Women’s Hospital. All samples are
949 stored with a code but no other identifiers. Dates of blood collection are recorded in the DCC and
950 are received but not stored at the Biorepository. Blood samples from the Biorepository may be
951 shared with internal study investigators as well as with external investigators, as approved by the
952 Ancillary Studies Committee.

953 If collected in the future, FFPE tissue blocks will also be stored in an established COPDGene
954 Biorepository at Brigham and Women’s Hospital, or at National Jewish Health.

955 The Genetic Analysis and the Sequencing and Bioinformatics Centers are located at Brigham
956 and Women’s Hospital, University of Colorado, Denver and Johns Hopkins University. These
957 centers receive DNA samples and genetic data for analysis. Samples and data are coded and have
958 no other identifiers associated with them.

959
960 The Biomarkers Center is located at National Jewish Health and works collaboratively with the
961 Biorepository sharing biospecimens to be used for analysis of biomarkers. Data will include
962 dates of sample collection.

963 The Subtyping Center is made up of investigators from the twenty clinical centers, who meet by
964 teleconference and collaborate on data analysis. Data shared to this Center will include geocodes
965 and location to the level of zip codes.

966
967 The Mortality Adjudication Center is located at National Jewish Health and is closely linked to
968 the Administrative Center. They will receive death certificates, subject medical records and when

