- 40 (2) Genome-wide association and DNA sequencing studies will identify genetic determinants
41 for COPD susceptibility that will provide insight into clinically relevant COPD subtypes.
- 42 (3) Distinct genetic determinants influence the development of emphysema and airway
43 disease.

44 **COPDGene Phase 3**

45 COPDGene has been funded for an additional five years by the US National Heart, Lung, and
46 Blood Institute as well as the COPD Foundation. In addition to the cross-sectional subject data
47 collected in the baseline and five year follow up COPDGene study visits, disease progression
48 and incidence of COPD in smokers are important additional endpoints for genetic association
49 studies. In Phase 1, we have completed enrollment of 10,371 subjects. In Phase 2, we have
50 completed 5,835 return visits and an additional 574 other follow up methods. For Phase 3, we
51 now propose to invite these subjects to return for a third evaluation ten years after their initial
52 visit to assess disease incidence and/or progression in COPDGene subjects.

53 **II. SPECIFIC AIMS**

54 The current specific aims for Phase 3 of COPDGene are included in this section.

55

56 **Specific Aim 1: Disease Progression**

57 All subjects who return for a 10-year visit and those who expire between the 5 and 10-year visits
58 will be analyzed to confirm prognostication of clinical disease progression. We estimate that
59 6,500 subjects will be analyzed in this aim; 4,500 subjects who return for a 10-year visit and
60 2,000 who expire before that visit.

61

62 **Specific Aim 2: Mortality and Incident Disease**

63 All 10,371 subjects enrolled in Phase 1 will be included to identify genetic, transcriptomic, and
64 proteomic determinants of susceptibility and progression of specific COPD subtypes. All these
65 subjects have had an initial visit but may or may not have visits at 5 and 10 years.
66 Through the longitudinal follow-up (LFU) program conducted twice a year since the initial visit,
67 we have obtained follow-up data from 82.3% of the original 10,371 subject cohort by a
68 combination of telephony, web survey or coordinator calls. We will continue LFU on all of the
69 original 10,371 subjects who are alive. All subjects will continue to be followed to assess vital
70 status. We will perform death searches at least yearly to identify subjects that have expired.
71 Death certificates, medical records and informant interviews will be obtained to determine cause

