72 of death.

73

74 **Specific Aim 3: Rapid Disease Progression Subtypes (Short Term Follow-up Study)**

75 To test high-risk subtypes for rapid COPD progression, approximately 800 subjects from the full
76 COPDGene cohort will participate. These subjects will be invited back for a Short Term Follow
77 up Study visit approximately one year after the Phase 3 visit.

78 Subjects participating in the Short-Term Follow-Up study will be identified by the Data
79 Coordinating Center and a list will be provided to each participating clinical center.

80 III. SUBJECT SELECTION- Phase 3

81 In summary, Phase 3 is the 10-year and 11-year (short-term follow up for applicable subjects)
82 return visit. Phase 3 is also the 5-year return visit for Non-Smokers enrolled in Phase 2.

83

84 All subjects to be studied have been enrolled in the Genetic Epidemiology of COPD Study
85 (COPDGene) in previous phases. As part of their original informed consent for COPDGene and
86 subsequent consent at the 5-year follow-up visit, subjects have provided consent to be re-
87 contacted for periodic follow-up and for other studies.

88 This project will invite all 10,371 subjects who are alive and still in the study who successfully
89 completed a Phase 1 visit for a Phase 3 study visit. At the time of writing this protocol, there are
90 1,573 deceased subjects. All non-smokers enrolled in Phase 2 will also be eligible to return for a
91 visit 5 years (\pm 6 month) after their first visit, in total 349 new non-smokers were enrolled in
92 Phase 2. This is a total of 10,720 subjects in the cohort. Phase 3 will be scheduled 10 years (\pm 6
93 months) after Phase 1 or 5 years (\pm 6 month) after Phase 2 (for new subjects enrolled in Phase 2).
94 There must be at least 3 years in between the Phase 2 and Phase 3 visits. Visits later than the
95 scheduled return visit *are* permitted. The Short-Term Follow-Up Study for rapid progressors
96 will occur approximately one year after the subject participates in the Phase 3 study.

97 A key component of the project is to establish contact with all of the previously enrolled subjects
98 who remain in the study or confirm the subjects are deceased. Clinical centers will utilize locally
99 stored contact information including secondary contacts to establish contact.

100 Eligible subjects will be contacted mail, email and/or phone and invited to participate in Phase 3

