671 trapping, six minute walk distance (6MWD), and health-related quality of life. Longitudinal
672 analyses will be performed with quantitative imaging phenotypes from the Phase 1, 2, and 3
673 visits. Key predictor variables to be assessed for these outcomes include age, gender, current
674 smoking status (at each visit), pack-years, baseline lung function, baseline CT emphysema and
675 airway measures, respiratory symptoms (e.g., chronic bronchitis, dyspnea), respiratory
676 medications, and co-morbid illnesses (including lung cancer and coronary artery disease).
677 Exacerbation frequency will be assessed as a predictor of primary outcome measures.
678 Transformations of CT and spirometric progression measures from among the Box-Cox family
679 of transformations will be considered to stabilize variance estimates across the ranges of CT
680 measurement values. We will compare the demographic and clinical characteristics of subjects
681 who have follow-up data to those subjects missing due to death and those subjects missing due to

682 loss to follow-up. Longitudinal analysis will be performed including time-dependent covariates
 683 such as change in current smoking status. Time-dependent covariates in these analyses include
 684 change in current smoking status and change in pulmonary medications. Disease progression and
 685 mortality will be simultaneously assessed to limit potential bias introduced by differential
 686 survival. This analytical approach considers the joint distribution of the vector of repeated
 687 measures (i.e., longitudinal progression of PFT abnormalities and CT measures) simultaneously
 688 with time to event (i.e., mortality) using the method developed by Hogan and Laird(10).
 689 The power to detect differences in 10-year changes between subtypes of COPDGen subjects
 690 was assessed for FEV₁, PERC15, adjusted lung density, and % gas trapping. These calculations
 691 used the mean and standard deviation (SD) with estimated changes in FEV₁(11), PERC15(12),
 692 adjusted lung density, and % gas trapping based on the 5-year follow-up visits. We assumed a
 693 significance level of 0.05 and equal variance of the change in each subtype group. These
 694 conservative calculations are based on comparing differences in rates of change for COPD-
 695 related phenotypes among two hypothetical groups of subjects ranging in size from 250 to 2000,

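### Specific Aim 1 admits every qualifying death but only those survivors who return at 10 years, so its analysis set is selected on the outcome and living non-returners are left out

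*Protocol*

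**What the plan says.** Section II, Specific Aim 1 (Disease Progression), defines its analysis set as "All subjects who return for a 10-year visit and those who expire between the 5 and 10-year visits", with the purpose of confirming prognostication of clinical progression. It estimates that "6,500 subjects will be analyzed in this aim": 4,500 returners and "2,000 who expire before that visit". The two descriptions of the deaths differ. The first limits them to the interval between the 5- and 10-year visits; the second counts any death before the 10-year visit.

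Specific Aim 2 (Mortality and Incident Disease) takes the whole cohort: "All 10,371 subjects enrolled in Phase 1 will be included to identify genetic, transcriptomic, and" proteomic determinants. It also provides for death searches at least once a year. Section III reports "1,573 deceased subjects" when the protocol was written. Section I says that Phase 2 "completed 5,835 return visits and an additional 574 other follow up methods".

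Section VII names all-cause mortality among the primary longitudinal outcomes. It says that disease progression and "mortality will be simultaneously assessed to limit potential bias introduced by differential" survival, using a mixture model for repeated measures and event times. It also plans to compare the characteristics of subjects with follow-up data with those of subjects missing through death and through loss to follow-up.

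**The concern.** Membership of the Aim 1 set depends on the outcome. Someone who dies in the window is in. Someone who lives is in only after a 10-year visit.

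The lack of a 10-year measurement cannot explain the difference, because the 2,000 decedents have none either. They contribute a baseline visit, a 5-year visit where one took place, and a date of death. A living non-returner has the same kind of record, with a date last known alive in place of a date of death. In a joint model of progression and survival, such subjects are ordinary censored observations.

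The protocol also gives reason to think that non-return is not random. Its home-visit provision in Section V is for subjects kept away by illness, disease progression or lack of transport.

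At stake is the purpose of the aim. Any absolute risk of death calculated within this set is too high. A predictor related to return among survivors can also acquire a spurious association with death.

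**Working it through.** **Inputs.** From Section II: 4,500 returners, 2,000 deaths, 6,500 in total, and a cohort of 10,371. From Section III: 1,573 known deaths. From Section I: 5,835 Phase 2 return visits. From Appendix A: 64 subjects excluded from analysis. The protocol does not give the number of deaths before year 5, the number of withdrawals, the number of living non-returners with a 5-year visit, or return rates by risk group. Where these are needed they are assumptions, shown as such.

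**Step 1: the protocol's own figure.** 4,500 + 2,000 = 6,500, which reproduces exactly. The death share in the set is 2,000/6,500 = 30.8%.

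**Step 2: the 2,000 are all deaths before the 10-year visit.**
- Cohort share: 2,000/10,371 = 19.3%. Ratio: 30.8/19.3 = 1.60.
- Survivors: 10,371 − 2,000 = 8,371, of whom 4,500/8,371 = 53.8% enter, against 100% of deaths.
- Odds of death: (2,000/4,500)/(2,000/8,371) = 1.86 times the cohort odds.
- Living subjects outside the set: 10,371 − 6,500 = 3,871.
- If the 64 excluded subjects are removed, and none is among the 6,500, the ratio is 10,307/6,500 = 1.59 and 3,807 are outside.

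**Step 3: the 2,000 are only deaths in years 5 to 10.** Let E be the number of earlier deaths. The number at risk is 10,371 − E, the ratio is (10,371 − E)/6,500, and the living subjects outside number 10,371 − E − 6,500. E is not stated. The range runs from 0 to 1,573, the upper end being the case in which every death known at the time of writing fell before year 5.

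| E (assumed) | At risk | Death share | Ratio | Living, outside |
|---|---|---|---|---|
| 0 | 10,371 | 19.3% | 1.60 | 3,871 |
| 500 | 9,871 | 20.3% | 1.52 | 3,371 |
| 1,000 | 9,371 | 21.3% | 1.44 | 2,871 |
| 1,573 | 8,798 | 22.7% | 1.35 | 2,298 |

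All the counts outside the set are before withdrawals.

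**Step 4: who could inform change in FEV1 or CT.** A change needs two visits. If all 4,500 returners had a Phase 2 visit (assumption), 5,835 − 4,500 = 1,335 Phase 2 visits remain for everyone else, decedents included. If 500 of the decedents had one, 835 are left for living non-returners; if 1,000 had one, 335 are left. If some returners skipped Phase 2, the 1,335 would be larger. The remaining non-returners contribute baseline and survival data only. The set as defined already accepts such subjects: at least 6,500 − 5,835 = 665 of its members had no Phase 2 return visit.

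**Step 5: effect on associations with death.** Suppose all deaths enter, and survivors enter with probability r1 in a high-risk group and r0 in a low-risk group. Then observed odds ratio = true odds ratio × r0/r1. With equal return rates the factor is 1. With assumed rates of 45% (high risk) and 60% (low risk) it is 0.60/0.45 = 1.33.

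**The case against.** The strongest reply is that mortality belongs to Aim 2, which includes all 10,371 subjects, and that Section VII nowhere confines all-cause mortality to the 6,500. This stands to the following extent. A reader might infer that the study's mortality results as a whole are inflated, and the documents do not support that. No section says that absolute death risk will be estimated in the Aim 1 set, so the inflation applies to any such risk that is calculated there. The reply does not rescue Aim 1, however. Aim 2 is directed at genetic, transcriptomic and proteomic determinants, whereas confirming prognostication is the task of Aim 1.

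A reader might also infer that everyone who died is included, that the inflation is 1.6-fold as a fact, or that some 3,900 living subjects with usable progression data are discarded. None of these follows. The defining sentence takes only deaths between the 5- and 10-year visits. The 1.60 and the 3,871 need the other wording, or no deaths at all before year 5. The count of living subjects also ignores withdrawals, and most of those outside the set probably lack a second visit.

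The protocol softens the selection. Late visits are allowed, home visits with spirometry are offered, and another centre or help with travel is possible. These measures raise the return rate, but home visits omit CT, and 4,500 is still the number expected to return.

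Finally, censoring or weighting for non-return is commonly left to a statistical analysis plan, which is not at hand. The composition of the set, however, is fixed in the protocol. The comparison of characteristics describes the imbalance without correcting it, and the joint model as described is aimed at death as the reason for missing measurements.

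**Conclusion.** The point holds. Specific Aim 1 conditions on death or return, and neither the joint model nor the descriptive comparison, as written, brings living non-returners into the analysis.

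The death share in the set exceeds that in the population at risk by a factor of about 1.60 if the 2,000 are all deaths before the 10-year visit. The factor is about 1.35 to 1.60 if they are only deaths in years 5 to 10, assuming 0 to 1,573 earlier deaths. The corresponding number of living subjects outside the set is 3,871, or 2,298 to 3,871, before withdrawals and the 64 exclusions. For change outcomes the loss is smaller, probably at most about 1,335 subjects, on the assumption that every returner had a Phase 2 visit.

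It would go too far to conclude that every predictor of non-return will be mistaken for a predictor of death or progression by a known amount. Odds ratios for death shift only if return among survivors differs by the predictor. The factor of 1.33 illustrates assumed return rates and is not an estimate. The direction and size of any bias in progression cannot be worked out from the protocol.

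Separately, the two descriptions of the 2,000 deaths are inconsistent. The 1,573 deaths known at the time of writing do not settle which is meant, since the 2,000 is a forecast.

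**What to change.** - Define the Aim 1 joint analysis set as all subjects at risk at a stated time origin: either all Phase 1 enrollees from their first visit, or all subjects known to be alive at the 5-year point. The two answer different questions, so the protocol should choose one.
- Let every subject contribute each available FEV1 and CT value. Right-censor living non-returners at the last date known alive, taken from longitudinal follow-up or the death searches.
- Keep 4,500 + 2,000 as the expected number with a Phase 3 outcome, not as the definition of the set.
- Reconcile the two descriptions of the deaths and state which ones the 2,000 counts.

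The cost is wording and some extra programming, with no new data collection. The small downside is that non-return is then assumed to be missing at random given the observed history.

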242 The below table summarizes each phase of COPDGene.

Phase 1- COMPLETED	Phase 2- COMPLETED	Phase 3a- current project	Phase 3b- Short Term Follow Up -current project	Phase 3 Modified COVID-19

Visit 1 for all subjects
 
n=10,371 enrolled
	
Phase 1 subjects followed up in Phase 2
 
n=6,409
	
Will invite all subjects alive and still in the study from Phase 1 back for Phase 3
	
Select group of up to 800 subjects characterized as rapid progressors from analysis of the Phase 2 data will be invited for a Short –Term Follow-Up study to occur approximately 1 year after the subject is due/returns for their Phase 3 (Phase 3a) study visit.
	
Will invite all subjects alive, still in the study from Phase 1, and have not yet completed a Phase 3 visit for a virtual visit over the phone to answer some of the questionnaires. Later, those subjects will be brought on-site to complete in-person portion of the visit.
 
All subjects will be invited to provide updated information and medical records through a new questionnaire about respiratory illnesses

	New Non-smoking Subjects enrolled n=349	All 349 nonsmokers enrolled in Phase 2 will be invited back for Visit 2 (5 year follow up)		and COVID associated illnesses or abnormal test results.
		New Nonsmokers will be recruited		

243
244 All subjects previously enrolled in Phase 1 have provided consent with their initial study
245 enrollment to be contacted again for further research studies. Subjects will be sent an invitation
246 letter advising them that funding has been provided for the Phase 3 visit and informing them that
247 they will be contacted to schedule an appointment. Information learned from previous phases of
248 COPDGene will be included in this initial contact.

249 A telephone call will be made to each subject to schedule a date for his/her next study visit and
250 ask them to bring the following to the study visit:

- 251 1) all of their current oral and inhaled medications,
- 252 2) names of any injectable study medications received on a regular basis,
- 253 3) social security number,
- 254 4) name, address, and phone number of their personal physician,
- 255 5) name, address, and phone of two other individuals likely to know the subject's
256 whereabouts, at least one of whom is a relative not living with the subject, and
- 257 6) driver's license or other identification to assure they are the individual previously

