495 14. In ever-smokers with COPD, hand grip strength is associated with computed tomography
496 markers of body composition and airway thickness, independent of body mass index and
497 emphysema. Higher hand grip strength is associated with lower exacerbation frequency
498 (36). Functional testing for hand grip strength measurements will be done using a Jamar
499 dynamometer. Subjects will be asked to squeeze the device with their dominant hand and
500 repeat the maneuver for a total of three measurements.

501 15. A urine pregnancy test will be performed on all pre-menopausal women prior to the CT
502 scan to confirm that they are not pregnant.

503 16. Medical Record Review: medical records may be reviewed when available and with a
504 signed release of records form documenting the subject's permission to obtain information

505 about lung diseases, cancer, other medical conditions, and to determine cause of death, in
506 the event of death.

507 17. If during the LFU call the participant answers that they had a COVID-19 diagnosis or
508 illness, the coordinator will call the participant to consent for and administer the short-
509 version COVID Questionnaire. If the phone consent is not possible, the coordinator will
510 send the LFU contact letter and the participant will call the coordinator to administer the
511 short-version COVID Questionnaire.

512 **Home Visit**

513 Previously enrolled COPDGene subjects who are unable to come to a COPDGene Clinical
514 Center to complete the Phase 3 visit due to illness, disease progression, or inability to be
515 transported to the Clinical Center, will be given the option of having a research coordinator
516 complete a partial study visit at the subject's place of residence.

517
518 If a COPDGene home visit is performed, it will include Home Visit Informed Consent and
519 HIPAA administration, pre and post-bronchodilator spirometry, blood draw, hand-grip strength,
520 sit-to-stand test, and completion of all study questionnaires and procedures, *except* the six-minute
521 walk, diffusing capacity, and CT scan.

522 **VI. OTHER PHASE 3 STUDY PROCEDURES**

523 **COVID-19 Adaptation**

524 During the COVID-19 pandemic, COPDGene will allow study sites to stop in-person visits to
525 protect both the subjects and staff. During this time, increased contact with the subject will occur
526 to track COVID-19-related illness. This will be tracked using a brief questionnaire that the

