	20	40	60	80
Odds ratio of 2.25	24.3	43.1	68.2	82.7
Odds ratio of 2.5	32.1	58.8	84.9	95.4

773
 774
 775 We will also perform epidemiological and Omics analysis in 800 subjects from the Short-Term
 776 Follow-Up Study Population. The relationships between the outcomes of interest (FEV₁ and
 777 adjusted lung density) of each of the three high risk groups compared to the reference group will
 778 be assessed using linear mixed models. Covariates in these analyses will include risk group, visit,
 779 age, gender, pack-years of smoking, current smoking status, and baseline FEV₁ % predicted. The
 780 relationship between changes in FEV₁ and changes in adjusted lung density will be assessed by
 781 including time-varying as well as subject mean values in the model as predictors. An
 782 unstructured covariance structure (or other appropriate structure) will be used in the model to
 783 account for repeated measures. We will adjust for multiple statistical testing by requiring
 784 $p < 0.01$ to demonstrate any significant association.

785
 786 The power estimates to detect differences in change in FEV₁ or adjusted lung density for the
 787 Short-Term Follow-Up Study are shown in **Table 4**. Two rapid progression groups will be tested
 788 for change in FEV₁ (High COPD Progression Score and Paraseptal Emphysema) and two rapid
 789 progression groups will be tested for change in adjusted lung density (High Risk Airway Disease
 790 Axis and Paraseptal Emphysema). Based on the five-year changes in those groups compared to
 791 non-high risk subjects, 200 subjects per group will provide excellent power to detect differences
 792 between the rapid progression and non-high risk groups over one year. Power to detect
 793 differences for RNA-Seq and proteomic biomarkers between 200 rapid progression and 200 non-
 794 rapid progression subjects was assessed. We will have 80% power to detect effect sizes > 0.6
 795 standard deviations, which will be adequate to detect useful biomarkers.

796

Outcome	Rapid Progression Group	Sample Size of Each Short-Term Follow-Up Group		
		100	200	300
FEV ₁ , ml/yr	High COPD Progression Score	100	100	100
	Paraseptal Emphysema	72	95	99
Adjusted Lung Density, per yr	High Risk Airway Disease Axis	100	100	100
	Paraseptal Emphysema	100	100	100

797
798
799
800
801
802
803
804
805
806

VIII. RISKS AND DISCOMFORTS

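### The Section IV table lets Phase 3b be timed from when Phase 3a was due, while Aim 3 and Section III time it from the attended visit, so the one-year interval behind Table 4 is not secured

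*Protocol*

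**What the plan says.** Three places in the Protocol set the timing of Phase 3b:

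- Section II, Specific Aim 3: "up Study visit approximately one year after the Phase 3 visit".
- Section III (Subject Selection): the short-term study "will occur approximately one year after the subject participates in the Phase 3 study".
- Section IV, table of phases, Phase 3b column: "approximately 1 year after the subject is due/returns for their Phase 3 (Phase 3a) study visit".

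Other provisions bear on how far these can diverge:

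- Section III schedules Phase 3 at 10 years ±6 months after Phase 1 and adds that visits later than the "scheduled return visit *are* permitted". It states no upper limit.
- The Section IV table takes up to 800 rapid progressors, who "from analysis of the Phase 2 data will be invited for a Short"-term follow-up visit. Selection therefore does not depend on Phase 3a data.
- Section VI (COVID-19 Adaptation) says that "COPDGene will allow study sites to stop in-person visits to" protect subjects and staff. The virtual visit has no spirometry or CT; both fall in the later in-person portion. The same section also brings subjects who report a respiratory exacerbation on surveys into 3b, without mentioning a completed 3a.
- Section VII claims power for differences "between the rapid progression and non-high risk groups over one year". Table 4 gives its outcomes in ml/yr and per year. The listed model covariates include visit; elapsed time is not among them.

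**The concern.** Aim 3 asks whether high-risk groups change faster than a reference group over a year. For each subject that needs spirometry and CT at Phase 3a and again about 12 months later. The wording in Aim 3 and Section III delivers this, because 3b cannot be timed until 3a has taken place. The table's wording does not: a site that counts from the due date complies with the table while departing from Section III.

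For an affected subject, the 3a-to-3b change then covers some interval other than a year, or there is no 3a measurement to subtract. In the second case the nearest earlier visit is Phase 2, nominally 11 − 5 = 6 years before 3b. If visits are compared by label alone, short and long intervals would be pooled as though each were one year.

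**Working it through.** **1. Interval under the due-date anchor.** Let L be the delay of Phase 3a in months past its due date, taking the 10-year anniversary as the due date (an assumption about what the table means). If 3b takes place 12 months after the due date, the 3a-to-3b interval is 12 − L.

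| L (months) | 12 − L (months) |
|---|---|
| −6 (early edge of window) | 18 |
| 0 | 12 |
| +6 (late edge of window) | 6 |
| +12 (permitted as a late visit) | 0 |

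Beyond L = 12, 3b would come before 3a. Under the attended-visit anchor the target interval is 12 months whatever L is.

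**2. Table 4's own figures.** The protocol gives no difference or SD for Table 4, so the table cannot be rebuilt from its inputs; only its internal consistency can be checked. Three of the four rows print 100% at 100, 200 and 300 per group. The fourth, FEV₁ in paraseptal emphysema, prints 72, 95 and 99%. Using the normal approximation for two equal groups, two-sided 0.05, and solving the n = 100 cell for effect/SD:

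- effect/SD = (1.960 + 0.583) × √(2/100) = 0.360
- power at n per group = Φ(0.360 × √(n/2) − 1.960)
- n = 200: 94.9% (printed 95); n = 300: 99.3% (printed 99)

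The row is consistent with two-sided 0.05. Two-sided 0.01 would give 97.1% and 99.8%, a worse fit.

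**3. Some subjects without a usable 3a.** The shares are assumptions, since the protocol gives none. The calculation treats such subjects as lost to the one-year contrast.

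| Share without usable 3a | n per group | Power, two-sided 0.05 | Power, two-sided 0.01 |
|---|---|---|---|
| 0% | 200 | 94.9% | 84.6% |
| 20% | 160 | 89.6% | 73.9% |
| 50% | 100 | 72.0% | 48.7% |

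The last column uses the p<0.01 threshold that Section VII sets for this analysis. Its first entry, 84.6%, reflects the threshold alone and not visit timing.

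**4. Shortened intervals.** Suppose the effect grows in proportion to time, the SD stays constant, and every subject has the same interval. At 200 per group and two-sided 0.05, power is 94.9% at 12 months, 76.9% at 9 months and 43.6% at 6 months. These are bounds for illustration, because not every subject would be late by the same amount.

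**5. With the attended-visit anchor** no printed figure changes; the 12-month interval that Table 4 presupposes is restored.

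**The case against.** The strongest reply is that this is a loose slash in a table introduced as a summary, set against two consistent statements in the text. Timing 3b from the actual return complies with the table just as well, and the due date may be meant only for forward planning. That stands: the table permits the problem without requiring it.

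A reader might also infer that the COVID provisions leave many subjects with a telephone visit only. The documents do not support that. Section IV plans for those subjects to come on site later, and the in-person column of the procedures table includes spirometry and CT. A home visit also yields spirometry, though no CT.

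A reader might infer that Aim 3 would have no one-year change to analyse. That holds for an affected subject, not for the aim. The planned linear mixed model keeps subjects with a missing visit through their other visits, and unequal intervals can be handled if actual dates are modelled. A statistical analysis plan may do so. It could not, however, recover a 3a measurement that was never taken.

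Finally, a reader might suppose that sicker subjects are late more often, so that the groups are affected unequally. This is plausible, but the protocol has no figure on it and the point does not rest on it.

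**Conclusion.** The inconsistency is real and bears on the Aim 3 endpoint, because a stated scheduling option can give an interval far from one year or leave no Phase 3a baseline. The interval range of 18 to 6 months, reaching zero at a 12-month delay, follows from the protocol's own window and late-visit rule, given the reading of due date above. The number of subjects affected cannot be known from the protocol.

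The power losses are for scale only. They rest on a back-solved effect/SD, on assumed shares, and on the single Table 4 row that is sensitive to sample size. With half the subjects lost, the other three rows would still print 100%, their n = 100 entry. The severity is moderate: the passages should be reconciled, but a reading that Aim 3 as a whole fails, or that the study cannot proceed without this change, goes further than the documents allow.

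**What to change.** Reconcile the Section IV table with Specific Aim 3 and Section III. Replace the due/returns wording with wording that starts the one-year clock at the completed Phase 3a spirometry and CT, counting the in-person portion of the modified visit as that completion. Apply the same starting point to the list that the Data Coordinating Center gives to the centers.

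Analyse the Aim 3 outcomes with the actual time elapsed between measurements rather than the visit label alone. Subjects seen at 3b without a 3a measurement may stay in the mixed model through their earlier visits, but should be reported separately from the one-year contrast. Reconciling the passages needs neither a particular tolerance around 12 months nor a bar on seeing subjects at 3b who never completed 3a.

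The cost is a one-line amendment to the table, an invitation-list rule and a time variable in the model. Some 3b visits will take place later. No procedures are added.
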